### 17.3.1.3 Other Secondary Analyses

### Investigator's Global Assessment (IGA)

The frequency distributions of IGA scores will be summarized by treatment group at Baseline, and at Days 8 and 15. The proportions of subjects considered a "treatment success" at Days 8 and 15 will be tabulated by treatment group. The treatment groups will be compared with respect to IGA treatment success rates at Day 8 using the CMH test stratified by center.

#### Clinical Signs of Psoriasis

The frequency distributions of the secondary efficacy endpoints, clinical signs of psoriasis (scaling, erythema, and plaque elevation), will be summarized by treatment group at Baseline, and at Days 8 and 15. The treatment groups will also be compared with respect to "treatment success" rates at Day 8 for each sign of psoriasis using the CMH test stratified by center. Subjects with Baseline scores of 0 or 1 will be excluded unless the corresponding sign score at Day 8 is >1.

#### Pruritus

Descriptive statistics of the 5-D Pruritus Scale scores will be provided by treatment group at Baseline and at Day 15. The treatment groups will be compared with respect to the change from Baseline in pruritus score using analysis of covariance with the model including terms for treatment and center with the Baseline pruritus score serving as the covariate.

#### BSA with Active Psoriasis in the Treatment Area

The changes from Baseline in the percent BSA with active psoriasis in the Treatment Area will be summarized for each treatment group with descriptive statistics at Days 8 and 15.

#### 17.3.2 Safety Analyses

### Dosing Compliance

Descriptive statistics will be used to summarize test article compliance for the Safety, ITT, and PP populations. Measures of test article compliance will include the duration of treatment, the total number of applications (determined from the doses reported by the subject), and the percent of expected doses applied. A subject will be considered compliant with the dosing regimen if the subject applies at least 80% of expected applications.

## Local Skin Reactions

The frequency distributions of the severity scores of the LSRs associated with topical application of corticosteroids including telangiectasia, skin atrophy, burning/stinging, folliculitis, and edema will be summarized by treatment group at Baseline, Day 8, and Day 15 for the Safety population.

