#### 3. OBJECTIVE

The primary objective of this study is to determine and compare the efficacy and safety of HBP Foam and the VEH Foam applied twice daily for two weeks (Study Day 15 + 3 days) in subjects with plaque psoriasis.

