- 6. Subject has used any systemic biologic therapy (i.e., FDA-approved or experimental therapy) within five (5) half-lives of the biologic prior to the Baseline Visit. Published or documented half-life of the product provided by the commercial supplier or Sponsor should be used to establish this value.
- 7. Subject had prolonged exposure to natural or artificial sources of ultraviolet radiation within 30 days prior to the Baseline Visit or is intending to have such exposure during the study which in the opinion of the investigator is thought to modify the subject's disease.
- 8. Subject has used topical body (excluding the scalp) psoriasis therapy (including coal tar, anthralin, steroids, retinoids, and vitamin D analogs) within 14 days prior to the Baseline Visit.
- 9. Subject has used emollients/moisturizers on areas to be treated within four hours prior to clinical evaluation at the Baseline Visit.
- 10. Subject is currently using lithium or Plaquenil (hydroxychloroquine).
- 11. Subject is currently using a beta-blocking medication (e.g., propranolol) or angiotensin converting enzyme (ACE) inhibitor at a dose that has not been stabilized, in the opinion of the investigator.
- 12. Subject has a history of sensitivity to corticosteroids or any of the ingredients in the test articles (see Section 6.1).
- 13. Subject is pregnant, lactating, or is planning to become pregnant during the study.
- 14. Subject is currently enrolled in an investigational drug or device study.
- 15. Subject has used an investigational drug or investigational device treatment within 30 days prior to the Baseline Visit.
- 16. Subject has been previously enrolled in this study and treated with a test article.
- 17. Subject is known to be noncompliant or is unlikely to comply with the requirements of the study protocol (e.g., due to alcoholism, drug dependency, mental incapacity) in the opinion of the investigator.

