### 7. RANDOMIZATION ASSIGNMENT

[figure not shown]
Subjects who are eligible for enrollment into the study will be randomized to receive HBP Foam or VEH Foam in a 1:1 ratio. The randomization scheme will be blocked by investigational site. At each site, subject kits (each containing three units) will be dispensed in ascending order as subjects are enrolled. At each site, the study staff will add the site number (provided to each site) and the subject number (starting with 001) to each kit label. The kit number dispensed to each subject will also be recorded on the source documents and CRFs. Treatment group designation will remain blinded until the final database is locked (unless unblinding is required as described in Section 15). Subject enrollment at the sites will be competitive. All subjects will apply the topical formulations as directed by the investigator.

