### 9.1 Visit 1 (Day 1): Screening/Baseline

At this visit, the investigator or designee will:

- Obtain a signed, written informed consent unless the subject signed a consent within the past 45 days.
- Complete review and documentation of the subject's medical history and demographic information.
- Record any concomitant medications and therapies.
- Confirm subject meets I/E criteria.
- Have subject complete washout from any prohibited medications, if necessary.
- Perform baseline activities of Visit 1 which should occur within 45 days of screening activities. For those subjects that required a washout period related to

exclusionary medications, the investigator needs to reaffirm the subject meets all protocol requirements at Baseline.

- Perform a limited physical exam. The limited physical exam will include vital signs, height, weight, head and neck, pulmonary, cardiac and abdomen examinations, and an assessment of motor and gait function.
- Perform a UPT for all WOCBP; the results must be negative for the subject to be enrolled into the study.
- Identify the psoriatic plaques to receive treatment during the study. At this visit, the psoriatic plaques in the Treatment Area must include

  BSA to fulfill study inclusion requirements. Lesions on the face, scalp, groin, axillae, and other intertriginous areas will not be included in the percent BSA calculation.
- Record the location of the plaques to be treated with the test article in the CRFs.
- Document the percent BSA with active psoriasis in the Treatment Area (see Section 10.4).
- Perform Baseline clinical evaluations (IGA, clinical signs of psoriasis, and pruritus; see Section 10) prior to application of the test article.
- Record Baseline LSRs prior to application of the test article.
- Perform photography (selected study sites only; see Section 11).
- If the subject meets the I/E criteria, randomize the subject by assigning lowest available study medication kit number in ascending order. At each site, the study staff will add the site number (provided to each site) and the subject number (starting with 001) to each kit label. The kit number dispensed to each subject will also be recorded on the source documents and CRFs.
- Weigh and dispense initial canister(s) of test article.
- Complete the Study Medication Accountability Log.
- Dispense bland emollient provided, as required.

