### 10.5 Local Skin Reactions (LSRs)

At every study visit, the investigator or designee will evaluate the severity (none, mild, moderate, or severe) of the following LSRs within the areas treated with test article known to be associated with topical application of corticosteroids:

- Telangiectasia
- Skin atrophy
- Burning/stinging
- Folliculitis
- Edema

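### The planned local skin reaction tables cannot show how many subjects developed a new or worsened reaction, and they may mask such reactions if Baseline symptoms clear faster on HBP Foam

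*Combined protocol and SAP*

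**What the plan says.** Section 3 gives the objective as to "determine and compare the efficacy and safety of HBP Foam and the VEH Foam applied twice daily for two weeks". Section 17.2.2 names LSRs, AEs and SAEs as the safety endpoints, without ranking them.

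Section 10.5 has the investigator or designee "evaluate the severity (none, mild, moderate, or severe) of the following LSRs within the areas treated with test article", for five reactions that include skin atrophy, burning/stinging and edema. Section 9.1 requires staff to "Record Baseline LSRs prior to application of the test article". Sections 9.2 and 9.3 repeat the grading at Day 8 and at the final visit. Each subject with follow-up therefore has a pre-dose grade and at least one later grade.

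The analysis text in Section 17.3.2, which the synopsis matches, is one sentence: the severity distributions "will be summarized by treatment group at Baseline, Day 8, and Day 15 for the Safety population". The documents give no shift table, change from Baseline, worst post-Baseline grade, definition of a treatment-emergent LSR or between-arm estimate. By contrast, Section 17.3.1.3 summarizes change from Baseline for percent BSA, and Section 14 starts AE collection at the first dose.

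**The concern.** Some subjects may enter with reactions already present. Exclusion 8 bars topical body psoriasis therapy, steroids included, only "within 14 days prior to the Baseline Visit", and exclusion 5 bars intralesional steroids for 90 days. Burning/stinging and edema may also come from the plaques themselves.

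A visit total is then a mixture of reactions that persisted from Baseline and reactions that began on treatment. Resolution of the old and onset of the new offset each other, and the total does not show by how much. A reaction graded at Day 8 and gone by Day 15 appears in the Day 8 table, but the number of subjects affected at any time on treatment cannot be recovered from the two tables.

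Early termination adds a smaller gap. Appendix 4 (A 4.5) provides for removal when irritation continues, and Section 13.2 calls for the final-visit procedures at withdrawal. No text says whether that early grade enters the Day 15 table, and the missing-data rules in Section 17.4 address only efficacy.

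What is at stake is how clearly the trial can report the local reactions that start or worsen under a super-potent steroid foam.

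**Working it through.** **Inputs.** The documents supply 200 subjects per arm (Section 17.1) and 1:1 allocation blocked by site (Section 7). They state no LSR rates, so every LSR rate below is an assumption. For simplicity each LSR is treated as present or absent, and new onset is counted at Day 15 in subjects free of it at Baseline.

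**Stated design figure.** The only figure to reproduce concerns efficacy. For 20% versus 9% (synopsis), exact two-sided Fisher power at 200 per arm is 0.858, against a stated 0.85. It reproduces, and nothing below changes it.

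**1. What the visit totals identify.** Let B and D be the numbers affected at Baseline and Day 15 in an arm of n, R the number resolved and N the number of new cases. Then D = B - R + N. With only B and D known, max(0, D - B) ≤ N ≤ min(D, n - B).
- B = 20, D = 20, n = 200: N lies between 0 and 20 (0% to 10%).
- B = 40, D = 40: N lies between 0 and 40 (0% to 20%).
- B = 40, D = 30: N lies between 0 and 30 (0% to 15%), although the total has fallen.

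**2. Between-arm difference.** Let b be Baseline prevalence (equal in expectation by randomization), p the proportion of Baseline cases that persist, and i the new-onset rate among unaffected subjects, with subscripts H (HBP) and V (vehicle).
- Visit-table difference = b(p_H - p_V) + (1 - b)(i_H - i_V).
- New-onset difference = (1 - b)(i_H - i_V).

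The two agree when p_H = p_V.

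**3. Equal persistence (p = 60% in both arms; i = 5% versus 1%).** Both differences are 0.9 × 4 = 3.6 points at b = 10%, and 0.8 × 4 = 3.2 points at b = 20%. Precision differs. At b = 10%:
- Visit tables: Day 15 prevalence is 0.060 + 0.045 = 0.105 versus 0.060 + 0.009 = 0.069. SD = √[(0.105 × 0.895 + 0.069 × 0.931)/200] = 2.8 points.
- New onset: 0.045 versus 0.009. SD = √[(0.045 × 0.955 + 0.009 × 0.991)/200] = 1.6 points.

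At b = 20% the SDs are 3.5 and 1.5 points. Simulation gave the same values.

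**4. Unequal persistence (p = 30% on HBP, 80% on vehicle; i as above).**

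| Baseline prevalence | Visit tables, HBP vs VEH | Difference | New-onset difference |
|---|---|---|---|
| 10% | 7.5% vs 8.9% | -1.4 points | +3.6 points |
| 20% | 10.0% vs 16.8% | -6.8 points | +3.2 points |

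**5. When the sign reverses.** This requires p_V - p_H > (1 - b)(i_H - i_V)/b. With i = 5% versus 1%, the gap in persistence must exceed 0.9 × 0.04/0.1 = 36 percentage points at b = 10%, or 0.8 × 0.04/0.2 = 16 points at b = 20%. At b = 5% it must exceed 0.95 × 0.04/0.05 = 76 points. Reversal therefore needs fairly common Baseline symptoms and a real difference in clearing; smaller gaps only shrink the apparent excess.

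**6. Chance imbalance at Baseline.** The 95% half-width is 1.96√[2b(1 - b)/200]: 4.3, 5.9 and 7.8 points at b = 5%, 10% and 20%. The planned Baseline table would show such an imbalance, but the plan has no analysis that allows for it.

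**The case against.** The strongest reply is that the trial is randomized and vehicle-controlled, and "The randomization scheme will be blocked by investigational site". Carry-over from earlier steroids and symptoms present at entry are balanced in expectation. The Day 15 contrast is an unbiased estimate of the net effect on LSR prevalence, which is a legitimate safety quantity. This stands. A reader might infer that carry-over cannot be separated from the effect of the foam, or that the safety objective cannot be answered; the documents support neither. Nor do they make LSRs the main safety endpoint, since Section 17.2.2 does not rank the three it lists.

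AE reporting is a second source of evidence. AEs count from the first dose (Section 14), medication intolerance is to be recorded as an AE (A 4.5), and AEs are summarized by severity and relationship by arm. This stands in part. The available text does not say that every new or worsened LSR becomes an AE; text may be missing there, so this is not held against the plan.

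Third, masking requires unequal clearing, which is plausible for burning/stinging and edema because they may follow the plaques. No such mechanism is argued for the other three reactions. This also stands, and it limits the masking point to those two. It does not affect the bounds in step 1, which apply to any LSR present in some subjects at Baseline.

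Randomization does not equalize clearing, because clearing happens after allocation. The sample size itself assumes that disease improves more often on HBP Foam (20% versus 9% success).

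**Conclusion.** The point holds in a limited form. The planned tables do not identify new or worsened LSRs within an arm: equal totals of 20 of 200 fit 0 to 20 new cases. They are a less precise basis for comparing the arms than within-subject change (SD 2.8 versus 1.6 points at an assumed 10% Baseline prevalence). They can understate or reverse an excess of new burning/stinging or edema if those symptoms clear faster on HBP Foam. Non-identification follows from the plan's wording alone; the precision and masking figures rest on assumed rates and show what is possible, not what is likely.

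The comparison of net prevalence remains valid, and no information is lost in data collection. The gap is in the analysis plan only and touches neither the primary analysis, alpha nor the sample size. Severity is minor to moderate.

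**What to change.** In Section 17.3.2 and the synopsis, keep the three by-visit distributions and add, for each LSR in the Safety population:

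- (a) a shift table by arm of Baseline grade against worst post-Baseline grade, stating that any early-termination visit grade is included;
- (b) the proportion of subjects whose worst post-Baseline grade exceeds their own Baseline grade, with the between-arm difference and 95% CI.

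State that (a) and (b) are interpreted alongside the by-visit distributions, AEs and SAEs. They should not replace these as the sole basis of the safety conclusion. Specify both before unblinding.

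This is a cheap improvement: two additional tables from grades already collected, with no new procedure or data.

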#### Adverse Events

Product Name: Halobetasol Propionate Foam, 0.05% IND: 107,302

Sponsor Name: Protocol: 122-0551-310; v2.0

All subjects enrolled in the study who were dispensed and applied test article at least once (Safety population) will be included in the safety analyses based on AE reporting. All AEs reported during the study will be listed, documenting onset, whether therapy was required, any change in test article dosing, severity, possible relationship to test article, and outcome. Verbatim terms on the CRFs will be linked to PTs and SOCs using the MedDRA mapping system. The PTs and SOCs will then be tabulated. All reported AEs will be summarized by the number of subjects reporting AEs, SOC, PT, severity, and relationship to test article by treatment.

#### Urine Pregnancy Testing

Results from the UPT at Screening/Baseline and Day 15 will be provided in a subject listing.

### Amount of Test Article Applied

The total amount of test article used will be calculated from the weights of the returned test articles. Descriptive statistics will be provided by treatment group for the total amount of test article used by each subject for the Safety, ITT, and PP populations.

#### 17.4 Imputation of Missing Data

The primary efficacy endpoint is defined as a success rate. Any subject who cannot be confirmed as a "success" is a treatment failure; therefore, missing data is imputed as treatment failure.

The key secondary efficacy endpoints will be the proportion of subjects rated a "treatment success" for each of the clinical signs of psoriasis (scaling, erythema and plaque elevation) at Day 15. Subjects without data at Day 15 will be considered treatment failures, i.e., to not have achieved "treatment success". Note that this definition includes subjects who drop out of the study prior to Day 15 for any reason.

#### 17.5 Sensitivity Analyses

Sensitivity analyses will be performed to investigate the impact of data imputation on the primary endpoint (IGA "treatment success" at Day 15). These sensitivity analyses will include repeating the primary analysis (IGA "treatment success" at Day 15):

- 1) in the population of subjects with observed data for the primary endpoint (i.e., the "complete cases" population);
- 2) in the per-protocol population;
- 3) assuming that subjects with missing data are responders ("treatment success");
- 4) assuming that subjects in the VEH Foam group with missing data are responders and that subjects in the HBP Foam group with missing data are treatment failures ("worst case"):
- 5) Using multiple imputation to impute missing values of the primary endpoint.

These analyses will be examined in conjunction with the reasons for dropout or the proportions of dropouts between treatment groups. Conclusions regarding the investigation of possible bias introduced by dropouts and/or the method of missing data imputation will be included in the final clinical study report.

For the sensitivity analysis based on multiple imputation, missing values of the primary endpoint will be imputed using the logistic regression methodology of SAS procedure MI. The logistic regression model will include the following independent variables: treatment and plaque elevation as the covariate. A minimum of 10 imputed data sets will be generated for this analysis. The MIANALYZE procedure of SAS will be used to combine the results.

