### 6.2.1 Test Article Application

At the Baseline Visit, a study staff member will demonstrate how to dispense the test article and instruct the subject on the proper application of the test article to the Treatment Area (as defined in Section 5).

Subjects should be instructed to wash their hands before and after each test article application. Instructions are as follows:

Subjects should apply a thin uniform film of the assigned test article twice daily (morning and night) to all psoriatic plaques in the Treatment Area for two weeks (Study Day 15 + 3 days). The subject should ideally allow approximately eight hours or more separation between dose applications; not wash the treated area for at least four hours following test

article application, and should not apply the test article within four hours prior to any study visit. Areas that should NOT be treated under any circumstances include any areas of active psoriasis on the face, scalp, groin, axillae, or other intertriginous areas. Occlusion of treated areas is prohibited.

At each follow-up visit during the study, the investigator or designee should review proper application of the test article to all lesions designated for treatment.

As the subject's psoriatic plaques improve or worsen, the amount of test article applied will likely decrease or increase, respectively. Subjects with extensive disease which would typically require more than 50 grams of test article per week should not be enrolled in this study. If the subject's disease becomes unmanageable because of these limitations, they should be discontinued from the study as treatment failures.

The standard bland emollient provided for study use is ONLY to be used by the subject to treat those anatomic locations that are excluded from treatment (i.e., face, scalp, groin, axillae, or other intertriginous areas). The emollient may be applied to these areas as frequently as the subject desires to treat his/her psoriasis. An investigator-approved medicated (non-steroid) shampoo can be used to treat scalp psoriasis.

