## 13.2 Subject Discontinuation

A subject may be withdrawn from the study prior to completion for any of the following reasons:

- Whenever the subject decides it is in the subject's best interest to withdraw. NOTE: if the subject decides to withdraw from the study due to an AE then it should be classified as withdrawal due to an AE.
- Whenever the investigator decides it is in the subject's best interest to be withdrawn

- AEs
- Worsening of condition or treatment failure (in the opinion of the investigator)
- Intercurrent illness which may, in the investigator's opinion, significantly affect assessment of clinical status
- Noncompliance
- Pregnancy
- Lost to follow-up
- Sponsor administrative reasons

If a subject withdraws from the study prematurely for any reason, complete the final visit procedures. When a subject is withdrawn from the study for a treatment-related AE (i.e., possibly, probably or definitely related as defined in Section 14), when possible, the subject should be followed until resolution or stabilization of the AE.

Subjects who are prematurely withdrawn or discontinued from the study will not be replaced.

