#### 17.3 Statistical Methods

All statistical processing will be performed using SAS® unless otherwise stated. Statistical significance for the primary efficacy endpoint will be based on a two-tailed test of the null hypothesis at the alpha=0.05 level of significance.

Efficacy analyses will be performed primarily for the intent-to-treat (ITT) population. Efficacy analyses using the per-protocol (PP) population will be in support of the ITT analyses.

The Safety population will include all subjects enrolled in the study who were dispensed and applied test article at least once. Subjects will apply their first application of test article in the clinic during their Baseline Visit on Day 1. Subjects enrolled in the study who were

randomized and dispensed the test article will be considered the ITT population. Subjects will be included in the PP efficacy analyses if they have completed the study without significant protocol deviations. Subjects who discontinue from the study prematurely due to treatment failure, as determined by the investigator, will also be included in the PP population as treatment failures.

Demographic and baseline characteristics will be summarized by treatment group for the ITT, PP, and Safety populations. Frequency counts and percentages will be reported for categorical data and the number of subjects with non-missing data (n), mean, median, SD, minimum and maximum will be reported for the continuous variables.

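### Section 17.5 does not use the reason for withdrawal, so subjects withdrawn as treatment failures without a Day 15 IGA can be recoded as successes (analyses 3 and 4) or imputed (analysis 5)

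*Combined protocol and SAP*

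**What the plan says.** Three places in the protocol treat withdrawal for lack of response as an outcome in its own right.

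- Section 6.2.1, after the 50 g per week limit, says of subjects whose disease cannot be managed within it that "they should be discontinued from the study as treatment failures".
- Section 13.2 lists "Worsening of condition or treatment failure (in the opinion of the investigator" among the reasons for withdrawal.
- Section 17.3 says that subjects who stop early for treatment failure, as judged by the investigator, "will also be included in the PP population as treatment failures".

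The primary rule (Sections 17.3.1.1 and 17.4) counts everyone without Day 15 data as a failure, whatever the reason.

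Section 17.5 then lists five sensitivity analyses. Analysis 1 is run "in the population of subjects with observed data for the primary endpoint" and analysis 2 in the per-protocol population. Analysis 3 is run "assuming that subjects with missing data are responders", in both arms. Analysis 4, labelled the worst case, is run "assuming that subjects in the VEH Foam group with missing data are responders", with missing HBP Foam subjects as failures. Analysis 5 is multiple imputation by logistic regression on "treatment and plaque elevation as the covariate". On interpretation the section says: "These analyses will be examined in conjunction with the reasons for dropout" or the proportions of dropouts between groups.

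**The concern.** Section 17.5 exists to show how far the primary result depends on what is assumed about outcomes nobody saw. A subject lost to follow-up is such a case. A subject whom the investigator withdrew for treatment failure is a different case: a Day 15 score of clear or almost clear is implausible, and the per-protocol definition already counts that subject as a failure. Analyses 3, 4 and 5 treat the two alike.

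If analysis 3 or 4 shows a clear loss of effect, part of the shift may come from relabelling investigator-judged failures and not from unknown outcomes. In analysis 4 the relabelling happens on VEH Foam only, so it always works against HBP Foam. What is at stake is how a robustness check reads in the study report. No claim of efficacy depends on it.

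**Working it through.** **The plan's own figure.** The Synopsis assumes 20% versus 9%, 200 per arm, Fisher's exact test, two-sided 0.05, power 0.85. Full enumeration gives an exact power of 0.858, so the figure reproduces. The expected successes are 0.20 × 200 = 40 and 0.09 × 200 = 18.

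**Status of one subject** withdrawn for treatment failure with no IGA counted as Day 15 data:

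| Analysis | HBP Foam | VEH Foam |
|---|---|---|
| Primary (17.3.1.1, 17.4) | failure | failure |
| 1, observed data | left out | left out |
| 2, per-protocol | failure | failure |
| 3 | success | success |
| 4 | failure | success |
| 5 | imputed | imputed |

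**Test used for illustration.** Unstratified chi-square without continuity correction, n = 200 per arm, a and b successes: z = [(a − b)/n] / √[p̄(1 − p̄)·2/n], with p̄ = (a + b)/(2n). For 40 versus 26: p̄ = 66/400 = 0.165, the standard error is √(0.165 × 0.835 × 2/200) = 0.0371, z = 0.07/0.0371 = 1.89, p = 0.059. The documents give no dropout or withdrawal counts, so every count below is an assumption.

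**Analysis 4** (HBP Foam stays at 40):

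| VEH successes after recoding | Difference, points | p |
|---|---|---|
| 18 | 11.0 | 0.0018 |
| 21 | 9.5 | 0.0082 |
| 24 | 8.0 | 0.029 |
| 25 | 7.5 | 0.042 |
| 26 | 7.0 | 0.059 |

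The p-value first exceeds 0.05 at 26, which is 26 − 18 = 8 recoded VEH subjects. The number of failure withdrawals needed is therefore 8 minus the other missing VEH subjects: 8 with no others, 5 with 3 others, 2 with 6 others. With 8 or more others, analysis 4 exceeds 0.05 even if failure withdrawals are kept as failures.

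**Analysis 3**, failure withdrawals given as HBP/VEH.

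- Six other missing per arm, 0/0: 46 versus 24, 11.0 points, p=0.0038.
- Six other missing per arm, 0/2: 46 versus 26, 10.0 points, p=0.0092.
- Six other missing per arm, 2/2: 48 versus 26, 11.0 points, p=0.0046.
- No other missing, 2/8: 42 versus 26, 8.0 points, p=0.033.
- No other missing, 2/10: 42 versus 28, 7.0 points, p=0.065.

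The difference depends on the imbalance between arms, and crossing 0.05 takes a large one.

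**Analysis 5**, expected difference with plaque elevation ignored, so that missing values take the observed rate of their arm.

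- Six other missing per arm, 0/2: as written 40/194 − 18/192 = 11.24 points. With the two kept as failures, 40/194 − 18/194 = 11.34 points. Change: 0.10.
- No other missing, 0/8: as written 40/200 − 18/192 = 10.63 points. With the eight kept as failures, 11.00 points. Change: about 0.37.

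**Stratification by center.** The planned test is the CMH test. For an assumed 20 centers of 10 per arm, with successes spread at random (5,000 draws), the median CMH p is 0.0018 for 40 versus 18, about 0.029 for 40 versus 24, and 0.060 for 40 versus 26. The unstratified figures are a fair guide.

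**The case against.** The strongest reply is that analyses 3 and 4 are deliberate bounds. The primary rule imputes failure for dropout of any kind, so reversing it for the same set of subjects is the matching stress test, and analysis 4 is openly labelled the worst case. It errs only against HBP Foam: it can make a robust result look fragile, but not the reverse. This stands. A reader might infer that analyses 3 and 4 are wrong and should be replaced. The documents do not support that.

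A reader might also infer that these subjects have a known Day 15 failure. They do not. Success is defined on the Day 15 IGA, whereas withdrawal for treatment failure is an investigator's opinion. Section 6.2.1 is also narrower than unmanageable disease in general, because it refers to the product limit. So success is implausible, but the score is unobserved. This is a reason to add a version and not to substitute one.

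The affected set may be small or empty. Section 13.2 asks for the final visit procedures after any early withdrawal, and Section 9.3 lets them occur early, so an IGA may exist. The plan does not say whether it counts as Day 15 data. The note in Section 17.3.1.1, which places dropouts before Day 15 among those without data, suggests that it may not.

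Finally, Section 17.5 already reads the results beside the dropout reasons or proportions. A count of reasons by arm would give the share of the analysis 4 shift due to failure withdrawals. That helps in part, but it changes no subject's value, gives no test result without the relabelling, and as worded could be met by proportions alone.

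**Conclusion.** The point holds as a modest improvement. Section 17.5 does not use a withdrawal reason that Section 17.3 uses for the per-protocol set. Analysis 4 is the one most exposed, analysis 3 is secondary, and analysis 5 barely moves (0.1 to 0.4 points in the examples). Analyses 1 and 2 are not at issue.

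A reader might take the p-values above 0.05 as a threat to the trial's conclusion. They are not: the primary and gatekeeping tests do not change, and no decision rule rests on analyses 3, 4 or 5.

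The sizes rest on assumed withdrawal counts, the planned success rates, and no IGA being counted as Day 15 data for these subjects. The documents neither support nor exclude counts of this order. Confidence is medium because the number affected is unknown.

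**What to change.** Add to Section 17.5, before the database is locked and treatment is unblinded:

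*In analysis 5, subjects withdrawn for worsening of condition or treatment failure without Day 15 data are kept as non-responders and only Day 15 IGAs missing for other reasons are imputed. Analyses 3 and 4 are reported as written, as outer bounds, and repeated with these subjects kept as non-responders.*

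The wording follows the single combined reason listed in Section 13.2. Analysis 1 stays the observed-data analysis.

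The cost is two sentences and two extra analysis lines. There is one real downside. The added version of analysis 4 is less conservative for HBP Foam, by 26 − 24 = 2 subjects or 1.0 point in the 2-withdrawal example and by 26 − 18 = 8 subjects or 4.0 points in the 8-withdrawal example. It also relies on a reason judged by the investigator. It should therefore supplement the stated worst case and not replace it.
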